As SNT-CRS-002 study was completed (Clinical Study Report version 1.0 dated 15 July 2019), the data collected in the natural history studies has now been checked for the estimate of the responder rate. Based on the combined data from 175 eyes in the two natural history studies (SNT-IR-006 and SNT-CRS-002), the estimated responder rate is below 22%, i.e. lower than the initially expected rate of 24%. Although the determination of the exact responder rate for the natural history studies requires final data from the LEROS study for matching purposes, it is reasonable to assume that the responder rate of the natural history studies is not higher than 22%. The sample size for LEROS study is therefore re-calculated using the same methods as in the original protocol (Version1.0, 29 January 2016). In order to reach a power of 90% for the comparison of the responder rates between the natural history studies (assumed to be 22% instead of 24%) and the LEROS study (assumed to be 40%, as defined in the protocol), evaluable data from altogether 110 eyes from the LEROS study is required. In order to account for a drop-out rate of 30% (as defined in the protocol), at least 80 patients (equal to 160 eyes) will be enrolled to the LEROS study.

The sample size calculation was done with nQuery Advisor version 8.3.

For the sample size for the eye treated >1 year after the onset of symptoms and the corresponding external natural history control group, the aim is to collect VA data from same number of eyes as for the primary objective in order to compare the patients treated ≤1 and >1 year since the onset of symptoms and to compare patients treated with Raxone >1 year since the onset of symptoms with the corresponding natural history control group, assuming sufficient natural history control data can be collected to generate the natural history control group as described in 8.3.2.

Study: SNT-IV-005

V1.0 07 June 2021

7 Statistical hypotheses

The primary aim of the analysis is to show the superiority of Raxone® (patients treated ≤1 year after onset of symptoms) versus matching NH IDE naïve patients in proportion of eyes with clinically relevant recovery of VA from BL or 12 month maintenance of BL VA better than 1.0 logMAR

H₀: Raxone® (patients treated ≤1 year after onset of symptoms) is not superior to matching NH IDE naïve patients in proportion of eyes with CRR of VA from BL or 12 month maintenance of BL VA better than $1.0 \log MAR$

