 H_1 : Raxone® (patients treated ≤ 1 year after onset of symptoms) is superior to matching NH IDE naïve patients in proportion of eyes with CRR of VA from BL or 12 month maintenance of BL VA better than $1.0 \log MAR$

A two-sided 95% confidence interval (CI) for the odds ratio (Raxone® versus NH IDE naïve) is used in the evaluation of the hypotheses. Superiority is shown if the lower limit of the two-sided 95% CI is greater than 1. This is equivalent to obtaining a p-value of less than 0.05 in the statistical test for the H_0 .

8 Analysis sets

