8.4 Natural History control set

The Natural History (NH) external control set for LEROS study is constituted by the combined data from CRS-1 and CRS-2. In order to ensure comparability between populations, the following criteria, based on LEROS inclusion/exclusion (section 5.4 and 5.5) criteria and patients included in the ITT population, are required for subjects to be included in the external NH (Natural History) control set out of all patients included in CRS-1 and CRS-2:

SNT-IV-005 Statistical Analysis Plan

Confidential

- Carriers of only one of the three major LHON mtDNA (G11778A, G3460A or T14484C)
- Age \geq 12 years;
- No other cause of visual impairment apart from LHON;
- Date of symptoms onset is defined (or at least month and year known);
- Onset of symptoms are less or equal to 5 years at BL visit;
- At least 2 VA assessments;
- VA assessments visit date must be defined (or at least month and year known).

The NH control set in conjunction with the ITT population will be used to evaluate efficacy endpoints defined in section 4.

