In the statistical analyses a p-value less than 0.05 will be considered as statistically significant. If not stated otherwise, all tests will be performed as two sided tests and two sided 95% confidence intervals will be produced for the treatment differences.

CRS-1, CRS-2 and LEROS data will be presented in separate listings (one per study).

Unscheduled or repeat assessments in LEROS will not be included in summary tables, but will be included in listings.

Otherwise specified, listings will be sorted by patient number and visit date.

Deviations from the statistical plan will be reported in the clinical study report, including the rationale for the deviation.

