11.1 Demographic and other Baseline characteristics

Variables: Table 11-1 shows which variables to analyse for the different analysis data sets.

Analysis method: Demographic and BL characteristics will be analysed by means of descriptive statistics. The start of the Raxone[®] treatment will be used as the BL (LEROS ITT).

Table shell structure is presented section 19.2.

Table 11-1 - Demographic and BL characteristics by analysis sets and subgroups

				Analys	is sets		
	Variable Type ¹	LEROS mITT / NH matched sets ²	Safety population	LEROS ITT	mtDNA subgroups ³	Age at BL subgroups ³	Best VA at BL subgroups ³
Demographics					J		
Gender	N	Х	Х	Х	Х	х	Х
Child bearing potential	N	-	Х	х	х	х	Х
Mutation	N	х	Х	х	Х	х	Х
Race	N	-	Х	х	Х	х	Х
Height	С	-	х	х	Х	х	Х
Weight	С	-	х	х	Х	х	Х
Age at BL	С	х	х	х	Х	х	Х
Baseline characteristics			^				
Age at 1 st symptoms onset ⁴	С	х	-	х	Х	х	х
Months since 1 st symptoms onset	С	х	-	х	Х	х	х
Months since most recent symptoms onset	С	Х	-	х	х	х	х

Number of symptomatic eyes per patient	0	х	-	Х	х	х	х
Eye with 1 st symptoms onset	N	х	-	х	Х	х	х
Delta onset (months) ⁵	С	Х	-	Х	х	x	×

¹ Variable Type: nominal (N), ordinal (O), continuous (C); ² Matched data sets (as defined in section 8.5) used in the calculation of 12 and 24 months endpoints evaluation; ³ Subgroups are to be analysed as defined in 9.3; ⁴ Age calculated as date of baseline visit minus date of birth, divided by 365.25; ⁵ Patients whose eyes have the same date of symptom onset will not be accounted

Listings: LEROS Safety population race, gender, weigh, height, age at baseline and LHON mtDNA will be listed, order by patient unique identification number.

For Natural History patients gender, age at baseline and LHON mtDNA will be listed, order by report survey, center and patient identification.

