12.1 Primary endpoint

Endpoint: Proportion of eyes with clinically relevant recovery (CRR) of visual acuity from Baseline (BL) or in which BL VA better than 1.0 logMAR was maintained at Month 12 in patients treated with Raxone® ≤1 year after the onset of symptoms, compared to matching external natural history control group. CRR definition is presented in section 16.

Analysis sets: Primary endpoint analysis will use all LEROS mITT eyes that are ≤1 year since onset of symptoms at BL and have the Month 12 assessment. External NH control set is generated as described in section 8.5.1 (Matching algorithm for the primary endpoint), using VA assessments within 12±3 months from BL.

Analysis method: The primary endpoint will be analysed using a logistic regression model. The binary response will be used as the dependent variable. The independent variables include the treatment group (Raxone® treated patients versus untreated control group), gender (male, female) and mutation group (G11778A, G3460A, T14484C) as fixed factors.

The difference between the Raxone® treated patients versus NH group will be estimated with odds ratio, two-sided 95% confidence intervals and two-sided p-values

```
proc logistic;
  class treatment gender mutation / param=ref;
  model CRB(event='1') = treatment mutation gender / link=logit clodds=pl;
  oddsratio treatment;
run;
```

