  class treatment gender mutation / param=ref;
  model CRB(event='1') = treatment gender mutation / link=logit clodds=pl;
  ods output ParameterEstimates = ParameterEstimates;
  ods output CLOddsPL = CLOddsPL;
run;
     STEP 5: calculate the logistic analysis combined results*/
proc mianalyze parms(classvar=classval)= ParameterEstimates.;
   modeleffects treatment gender mutation;
run;
```

```
STEP 6: calculate the combined results odds ratio */
/* Transform estimates */
data calculated odds ratio 1;
   label or_value = 'Log odds ratio value'
        or stderr = 'Log odds ratio SE';
  set CLOddsPL;
     or value = log(OddsRatioEst);
     or_stderr= (log(uppercl)-log(lowercl))/(2*1.96);
run;
    Combine transformed estimates */
proc sort data= calculated_odds_ratio_1; by Effect; run;
proc mianalyze data= calculated_odds_ratio_1;
       by Effect;
       modeleffects or_value;
       stderr or_stderr;
       ods output ParameterEstimates = calculated odds_ratio_2;
     run;
     Back-transform combined values */
data calculated odds ratio 3;
   label estimate back = 'Odds ratio'
        lcl back = 'LCL Odds ratio'
        ucl_back = 'UCL Odds ratio';
       set calculated_odds_ratio_2;
       estimate back = exp(estimate); *pooled odds ratio;
       lcl_back=estimate_back*exp(-1.96*stderr); *pooled lower limit;
       ucl_back=estimate_back*exp(+1.96*stderr); *pooled upper limit;
     run;
```

Through inverse probability of treatment

Propensity score will be calculated by means of logistic regression with treatment as dependent variable. Independent variables include gender (male, female), mutation group (G11778A, G3460A, T14484C), age, time since symptoms onset in months and VA at BL (logMAR) as factors.

The same primary model as described above will be applied with the inverse probability weight.

```
SAS code to calculate the propensity score (values: Raxone® treated patients = 1; NH = 0)
proc logistic data=CRB dataset;
  class gender mutation / param=ref;
  model treatment(event='1') = gender mutation age time onset bl va;
  output out=psdataset pred=ps;
run;
data analysis dataset;
  set psdataset;
  if treatment = 1 then ps weight = 1/ps;
  else if treatment = 0 then ps weight = 1/(1 - ps);
run;
SAS code to proceed with the endpoint regression analysis
proc logistic data= analysis dataset;
  class treatment gender mutation / param=ref;
   model CRB(event='1') = treatment gender mutation / link=logit clodds=pl;
  oddsratio treatment;

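### The model that decides superiority omits age at baseline, so the primary odds ratio is biased if age predicts response and the age mix differs between LEROS and the surveys

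*SAP*

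**What the plan says.** SAP 7 ties the primary conclusion to one estimate: "Superiority is shown if the lower limit of the two-sided 95% CI is greater than 1". SAP 12.1 obtains that odds ratio from a logistic regression on treatment, "gender (male, female) and mutation group (G11778A, G3460A, T14484C) as fixed factors", and the SAS code there has the same terms. Protocol 9.4.2 has treatment and mutation only, so the SAP has already added one baseline factor. SAP 12.2 analyses the secondary comparisons with the control group by the same method.

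Age appears in four other places:

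- **SAP 8.4** gives the entry rule for controls: "criteria, based on LEROS inclusion/exclusion (section 5.4 and 5.5) criteria and patients included in the ITT population, are required for subjects to be included". The only age condition among these criteria is a minimum of 12 years.
- **SAP 12.1.1** builds a propensity score from gender, mutation, "age, time since symptoms onset in months and VA at BL (logMAR) as factors". The outcome model is then the primary model again, weighted, as a sensitivity analysis.
- **SAP 9.3** plans age subgroups (<18, 18 to <35, ≥35), within the LEROS ITT population only.
- **SAP 11.1** tabulates age at baseline for the matched sets and adds: "For Natural History patients gender, age at baseline and LHON mtDNA will be listed". The variable therefore exists in both groups.

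SAP 8.5.1 does not use age. It takes, for each control eye, the observation whose time since onset is nearest the LEROS average, and drops eyes more than 6 months beyond that average.

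**The concern.** LEROS is a prospective trial and the controls come from case record surveys, so nothing in the design makes their age distributions alike. The SAP considers age worth balancing when it builds the propensity score. Of the five variables in that score, the primary model contains two (gender and mutation), and the matching addresses a third (time since onset) through an average. Neither the model nor the matching addresses age or baseline VA.

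If younger and older patients respond differently and the groups differ in age, part of the age effect appears as a treatment effect in the one estimate that decides superiority. A discrepant weighted analysis would not alter that conclusion under SAP 7.

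**Working it through.** **1. The plan's own figure.** SAP 6 gives the aim of the calculation: "In order to reach a power of 90% for the comparison of the responder rates between the natural history studies". It takes 22% for controls and 40% for LEROS, and arrives at 110 LEROS eyes. The control data are 175 eyes. For a two-proportion test with pooled variance at two-sided 0.05:

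- Pooled rate = (175 × 0.22 + 110 × 0.40)/285 = 0.2895.
- SE under the null = √[0.2895 × 0.7105 × (1/175 + 1/110)] = 0.0552; SE under the alternative = √[0.22 × 0.78/175 + 0.40 × 0.60/110] = 0.0562.
- Power = Φ[(0.18 − 1.96 × 0.0552)/0.0562] = 89.9%.
- Drop-out: 110/0.7 = 157.1, so 158 eyes or 79 patients, consistent with at least 80.

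The figure reproduces. At these sizes, 32.5% against 22% (odds ratio about 1.71) is just significant.

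**2. Illustrative bias with no drug effect.** These inputs are assumptions, because the documents supply none:

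- Response by age band (<18, 18 to <35, ≥35): 28/22/17% (mild) or 35/23/14% (moderate).
- 15% aged <18 in both groups.
- Share aged ≥35: 25-35% in LEROS, 45-50% in controls.
- 110 and 175 eyes, treated as independent.

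Marginal rate = sum over bands of share × band rate. For the mild effect with the widest gap:

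- LEROS: 0.15 × 28 + 0.60 × 22 + 0.25 × 17 = 21.65%.
- Controls: 0.15 × 28 + 0.35 × 22 + 0.50 × 17 = 20.40%.
- Odds ratio = (0.2165/0.7835)/(0.2040/0.7960) = 1.08.

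False superiority ≈ Φ[ln(OR)/SE − 1.96], with SE = √[1/(110·p_T(1−p_T)) + 1/(175·p_C(1−p_C))]. Here this is Φ(0.0753/0.298 − 1.96) = 4.4%.

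| Age effect | Aged ≥35, LEROS vs controls | Rates | Spurious OR | False superiority |
|---|---|---|---|---|
| Mild | 35% vs 45% | 21.15% vs 20.65% | 1.03 | 3.2% |
| Mild | 25% vs 50% | 21.65% vs 20.40% | 1.08 | 4.4% |
| Moderate | 35% vs 45% | 21.65% vs 20.75% | 1.06 | 3.8% |
| Moderate | 25% vs 50% | 22.55% vs 20.30% | 1.14 | 6.6% |

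Simulation agrees within about 0.1 percentage point. The nominal upper-tail rate is 2.5%. Swapping the groups in the widest-gap rows gives odds ratios of 0.93 (mild) and 0.87 (moderate).

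**3. Does a covariate remove it?** This check used continuous age with an assumed SD of 14 years, LEROS 5 years younger, no drug effect and 2,000 simulated trials per case.

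| Response OR per 10 years | Without age: OR, false superiority | With age: OR, false superiority |
|---|---|---|
| 0.8 | 1.10, 5.2% | 0.98, 1.7% |
| 0.7 | 1.18, 9.0% | 0.99, 3.0% |

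**4. Is the weighted analysis a substitute?** It removes the bias: the estimates were 0.98 and 1.00 in the same two cases. But SAP 12.1.1 puts unstabilised weights into PROC LOGISTIC with no robust variance, so each group carries a total weight of roughly 285 eyes. With ages balanced, no drug effect and age as the only propensity variable, it declared superiority in 10.2% of simulated trials against 2.5%.

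**The case against.** The documents tie response to mutation and time since onset; the plan models the first and matches on the second. No section says that response depends on age. Protocol 1.1 describes LHON as typically a disease of young adults, which makes a large share of controls aged 35 or over, well above LEROS, hard to support. Age is not ignored either: it is in a pre-specified weighted analysis and tabulated for the matched sets, so an imbalance would be visible. Baseline VA is arguably the larger omission, because it determines which eyes can meet the maintenance component of the endpoint.

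Most of this stands and limits the point. A reader might infer from the propensity list that the SAP declares age a confounder. It does not: it lists age as a balancing variable, and the 9.3 subgroups are within LEROS only. A reader might also infer that any age difference passes directly into the odds ratio. That requires age to predict response beyond what gender, mutation and onset matching already carry.

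These arguments do not show that the deciding odds ratio is protected. A descriptive table does not adjust it, and the weighted analysis has no stated role in the decision.

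**Conclusion.** The point holds conditionally. The deciding model omits a baseline variable that the SAP itself uses to balance these groups and holds for both. Bias requires both an age imbalance and an age effect on response. The documents quantify neither, so its size and direction are unknown.

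Under the assumptions in step 2 of the working, the spurious odds ratio is about 1.03-1.08 (mild) or 1.06-1.14 (moderate), with false superiority of about 3-4.5% or 4-7%. These are crude odds ratios for independent eyes. If LEROS is older the bias works against the drug; with balanced ages there is none.

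A reader might expect a larger distortion. The moderate case reaches 1.27 and 12.8% only with a further imbalance under 18 (25% of LEROS against 10% of controls). An odds ratio of 1.60 with 40% false superiority needs a 10-year age gap and a response odds ratio of 0.6 per 10 years. The documents support neither scenario.

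The change is worth making because it is cheap and is credible only if specified in advance.

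**What to change.** Before database lock, pre-specify age at baseline as a covariate in the SAP 12.1 logistic model, either continuous or in the 9.3 bands. For controls, use age at the selected natural history baseline. Carry the term into the models that reuse 12.1: the 12.2 comparisons, the multiple-imputation analyses and the weighted outcome model. Decide at the same time whether baseline VA and time since onset, the other propensity variables missing from the primary model, should enter too. Record the change from the protocol model in SAP 14.

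The cost is SAP wording, a small amount of programming and at most 2 degrees of freedom for age; no new data are needed. The present model has four non-intercept parameters (treatment 1, gender 1, mutation 2), so age bands make six. Expected responder eyes at the planned rates are 0.40 × 110 + 0.22 × 175 = 82.5, about 82, which makes this feasible. Paired eyes are correlated, so the effective information is smaller than that count suggests. The sample-size calculation compares two proportions and does not change.

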1.1 Background

Leber's Hereditary Optic Neuropathy

LHON is a maternally inherited loss of vision due to atrophy of the optic nerve. More than 90% of individuals with LHON harbour one of three point mutations in mitochondrial DNA (mtDNA) (G11778A, T14484C, G3460A) affecting genes encoding complex I subunits of the respiratory chain (Mackey 1996, Newman 2013). It typically presents in young adults, mostly men, as painless acute or subacute visual failure of both eyes in quick succession. The estimated prevalence is approximately 2.2 per 100,000 (Mascialino et al., 2012) and LHON is thus an Orphan Disease according to EU and US criteria. Clinically, the acute phase of the disease begins with blurring of central vision and colour de-saturation that affect both eyes. After the initial symptoms, both eyes are usually affected within two to four months from disease onset. Within 12 months of visual loss in one eye, over 97% of patients will have second eye involvement. The central visual acuity deteriorates to the level of counting fingers in up to 80% of cases. Following the nadir, acuity may improve. The degree of improvement is dependent, in part, also on the precise genetic mutation of affected patients. With disease progression, individuals then proceed into the atrophic phase and are usually legally blind for the rest of their lives with a permanent large centrocecal scotoma (Sadun et al., 2011).

Idebenone 2-(10-hydroxydecyl)-5,6-dimethoxy-3-methyl-cyclohexa-2,5-diene-1,4-dione has been suggested to be effective in by-passing the complex I deficiency resulting from the mtDNA point mutations and maintaining cellular energy production by stimulating the alternative pathway through complexes II and III (Haefeli et al., 2011). This activity may also reduce the production of reactive oxygen species (ROS) associated with complex I deficiency and to protect cell membranes and mitochondria from oxidative damage. This provides a strong rationale for its use in LHON (summarized in Gueven and Faldu, 2013; Gueven, 2014).

Detailed information on the medicinal product and on non-clinical data is available in the Investigator's Brochure (IB).

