9.4.2 Efficacy Evaluation

The primary analysis will be based on Intention-To-Treat principle as change from Baseline.

The primary endpoint will be analysed using a logistic regression model. The binary response will be used as the dependent variable. The independent variables include the treatment group (idebenone treated patients versus untreated control group) and mutation group (G11778A, G3460A, T14484C). The difference between the idebenone treated patients versus untreated control group will be estimated with odds ratio estimates, 95% confidence intervals and two-sided p-values.

All patients who have at least one post-baseline assessment at 12±3 months after Baseline will be included in the primary analysis. This approach is chosen due to the lack of pre-defined visit structure in the control dataset. As a sensitivity analysis, the impact of incomplete data will be assessed by analysing the primary endpoint with a generalized linear mixed model. For this purpose, the SAS GLIMMIX procedure for binomial data with logic link will be used to estimate the treatment differences. Factors similar to the ones used for the primary endpoint will be included in the model. The data from the control dataset will be classified as visits by selecting the assessment which is closest to 6, 12, 18 and 24 months from all assessments conducted within a window of ±3 months. The treatment difference at Month 12 will be estimated using contrasts.

The secondary endpoints based on counts of eyes/patients will be analysed with methods similar to the primary endpoint.

The baseline VA will be used as a covariate and treatment group and mutation as fixed factors. A mixed model for repeated measures (MMRM) will be used to assess the impact of incomplete data. The responder status (CRR or no CRR) will be used as independent variable instead of the treatment group, as this data are not available in the control dataset.

At least the following subgroups will be analysed:

• Each primary LHON mtDNA mutation separately (G11778A, G3460A, T14484C)

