13.8 Other safety variables

No other safety data are to be analysed.

V1.0 07 June 2021

14 Deviations from the analyses planned in the current study protocol

There are currently no deviations from the CRS-1 CSP (version 1), CRS-2 CSP (version 1.0) and SNT-IV-005 CSP version 3.0 dated 06 March 2019 and SNT-IV-005 CSP addendum COVID-19 version1.0 dated 29 May 2020

15 Data analysis procedures

Statistical data analysis will be performed by 4Pharma Ltd according to current SAP.

Statistical analysis, tables and patient data listings will be performed with SAS® version 9.4 or higher for Windows (SAS Institute Inc., Cary, NC, USA).

16 Definitions

2nd eye onset

Most recent affected eye at Baseline.

Baseline (BL)

LEROS BL

NH BL

Best Visual Acuity

VA of the eye with best logMAR at the visit. However, if both eyes are off-chart, regardless of the VA, both eyes are considered as best eye.

Note: best eye at BL may not be the same as best eye at 6, 18 and 24 months or last assessment.

Clinical Relevant Benefit (CRB)

Defined as the composite of CRR and CRS, i.e, if the eye/patient has a CRR and/or a CRS then the eye/patient has also a CRB.

Clinical Relevant Recovery (CRR)

CRR is defined as improvement

or

- from "off-chart" (the equivalent of CF, HM, LP or NLP) VA to at least 1.6 logMAR value
 - of at least 0.2 logMAR value within "on-chart". Clinical Relevant Stabilization (CRS)

Is defined as maintenance of VA <1.0 logMAR in eyes with VA <1.0 logMAR at BL.

Clinical Relevant Worsening (CRW)

For any "on-chart" VA, CRW is defined as the disability to read at least 10 additional letters (equivalent to two chart lines) or a worsening to off-chart values (the equivalent of CF, HM, LP or NLP).

SNT-IV-005 Statistical Analysis Plan

Confidential

Delta onset

Is the time between symptoms onset of both eyes: date 2nd symptoms onset – date 1st symptoms onset. Patients will not be considered for calculating Delta onset if only one eye is affected or both eyes have the same date of symptom onset.

Months in Treatment

Months in treatment is only applied to LEROS patients. It is defined as time since BL to last follow-up during treatment period.

Nadir

Is the defined when VA reaches its worst point (highest logMAR or off-chart value). Time of nadir is the first time that nadir is reached.

Off-Chart

It is considered off-chart any VA entered as

- CF, HM, LP or NLP
- Any value above 1.68 logMAR

Patients ≤1 year after the onset of symptoms

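### The logistic model that decides superiority leaves out baseline visual acuity, although one route to response depends on it and no rule balances it between LEROS and the natural-history controls

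*SAP*

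**What the plan says.** - **Decision rule (SAP 7).** "Superiority is shown if the lower limit of the two-sided 95% CI is greater than 1". The odds ratio is that of treated versus natural-history eyes.
- **Model (SAP 12.1).** "model CRB(event='1') = treatment mutation gender / link=logit clodds=pl". The only terms are treatment, mutation and gender.
- **Response (SAP 16).** Clinically relevant benefit (CRB) is recovery (CRR), stabilisation (CRS), or both. Stabilisation "Is defined as maintenance of VA <1.0 logMAR in eyes with VA <1.0 logMAR at BL".
- **Eligibility.** LEROS asks for impaired acuity in affected eyes and sets no logMAR level (SAP 5.4). On acuity data, the natural-history set asks for "At least 2 VA assessments" with known dates, again with no level (SAP 8.4).
- **Control selection (SAP 8.5.1).** Any VA observation with a follow-up at 12±3 months may serve as a control baseline. The choice among them is made on time since onset alone.
- **Where baseline VA does appear.** It enters the propensity score of the weighted sensitivity analysis in SAP 12.1.1, with "age, time since symptoms onset in months and VA at BL (logMAR) as factors". It is described by group in Table 11-2 and defines LEROS subgroups in SAP 9.3. Protocol 9.4.2 also states: "The baseline VA will be used as a covariate and treatment group and mutation as fixed factors". It does not name the endpoint.

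**The concern.** Baseline VA helps to define the outcome. An eye at 0.8 logMAR can respond by improving or by staying below 1.0; an eye at 1.3 logMAR or off-chart can respond only by improving. Two groups with different shares of eyes below 1.0 logMAR can therefore differ in response rate when the drug does nothing.

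Randomisation would balance those shares on average, but here nothing in the design does so. The direction cannot be read from the documents either. Better eyes have an extra route to response, but they also have further to fall: "The central visual acuity deteriorates to the level of counting fingers in up to 80% of cases" (Protocol 1.1). At stake is whether the odds ratio in SAP 7 measures the drug or the mix of eyes.

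**Working it through.** **Inputs from the documents (SAP 6 and 7).** 110 evaluable LEROS eyes, 175 natural-history eyes, response 22% (control) and 40% (LEROS), 90% power, two-sided 95% interval.

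**The plan's own figure.** No allocation ratio is stated, so I take 175 as the control number.
- Pooled rate: (110×0.40 + 175×0.22)/285 = 0.2895.
- Standard errors of the difference: 0.0552 under the null, 0.0562 under the alternative.
- (0.18 − 1.96×0.0552)/0.0562 = 1.28, which is 89.9% power. Solving for 90% gives 111 eyes, so the stated 110 reproduces.

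**Assumed inputs.** The documents give neither the share of eyes below 1.0 logMAR nor their response rate. I assume shares of 20% to 40%, log odds ratios of +1.5, +0.75 and −0.75 for such eyes against the others, 22% control response, no drug effect and independent eyes.

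**One case by hand: +1.5, 40% of LEROS and 20% of control eyes below 1.0.**
- The control rate of 22% requires 0.2·p1 + 0.8·p0 = 0.22 with odds(p1) = e^1.5 × odds(p0). This gives p0 = 0.160, p1 = 0.460.
- LEROS rate: 0.4×0.460 + 0.6×0.160 = 0.280.
- Odds ratio: (0.280/0.720)/(0.22/0.78) = 1.38; log 0.322.
- Standard error: √[1/(110×0.280×0.720) + 1/(175×0.22×0.78)] = 0.280.
- P(lower limit > 1) = P(Z > 1.96 − 0.322/0.280) = 21%.

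With the shares reversed (20% and 40%), p0 = 0.1175 and p1 = 0.374. The LEROS rate is 0.169, the odds ratio 0.72 and false superiority 0.1%.

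**Simulation of the current model** (5,000 trials per case): odds ratio / false superiority.

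| Share <1.0, LEROS/control | +1.5 | +0.75 | −0.75 |
|---|---|---|---|
| 40/20 | 1.39 / 22% | 1.16 / 8% | 0.87 / 0.7% |
| 30/20 | 1.18 / 9% | 1.09 / 5% | 0.93 / 1.5% |
| 25/25 | 1.00 / 2.4% | 1.00 / 3.1% | 1.00 / 2.6% |
| 20/30 | 0.85 / 0.8% | 0.92 / 1.8% | 1.07 / 4% |
| 20/40 | 0.72 / 0.1% | 0.84 / 0.7% | 1.14 / 7% |

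**Which form of baseline VA removes the shift?**
- *Category alone.* It restores an odds ratio of 0.99–1.01 in all 15 cases above, but there the truth was built from those categories. When LEROS eyes have better acuity within categories, it leaves an odds ratio of 1.23 and 8.9% false superiority.
- *Linear logMAR alone, as in the propensity score.* It misses a step at 1.0. With the weights as printed, the weighted analysis gives an odds ratio of 1.09 at 40/20 and 0.88 at 20/40 under log odds ratio +1.5.
- *Category plus linear logMAR.* Odds ratio 1.00–1.01 and false superiority 2.1–3.0% in every case tried, with no loss of power.

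**The weighted analysis as printed.** SAP 12.1.1 sets, for example, "if treatment = 1 then ps weight = 1/ps", and 1/(1−ps) for controls. Each group's weights sum to about N = 285, together about 2N. Model-based errors then treat each group as 285 eyes. With no imbalance:
- true to reported variance: (1/110 + 1/175)/(2/285) = 2.11, and √2.11 = 1.45;
- P(Z > 1.96/1.45) = 8.9%; simulation gives 8.6–9.2%;
- weights rescaled to sum to 285 give a ratio of (1/110 + 1/175)/(2/142.5) = 1.05, hence P(Z > 1.91) = 2.8%; simulation gives 2.5–2.8%.

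**The case against.** **The plan already adjusts for baseline VA in the weighted analysis, and Table 11-2 will show any imbalance.** Both are true, and the weighted analysis is real mitigation; where response is linear in logMAR it works well once its weights are normalised. But it does not decide superiority, its printed variance is too small, and a descriptive table does not change the odds ratio.

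**No imbalance is shown, and the magnitudes are assumed.** This stands. A reader might infer from the 22% that the plan favours the drug. The documents do not support that: the same mechanism gives 0.1% when the mix is reversed, and the sign of the acuity effect is itself unknown. The 175 control eyes are also not the final matched number, which SAP 6 says depends on final LEROS data.

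**Selecting on time since onset may balance acuity indirectly, because acuity evolves with time.** It may do so in part. The documents give no figure, and eyes at the same time from onset need not have the same acuity.

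**The protocol already requires baseline VA as a covariate.** A reader might infer that the SAP dropped a promised primary covariate. Protocol 9.4.2 does not bear this out: its primary model has only treatment and mutation, and the covariate sentence follows the secondary endpoints and precedes one on a repeated-measures model.

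**Conclusion.** The concern holds in this form. The deciding model omits a baseline variable that partly defines response, in a non-randomised comparison where no rule balances it. The mechanism follows from the text; its realised size and direction do not. Under the assumed 20-point differences and a log odds ratio of 1.5, the null odds ratio runs from about 0.7 to 1.4 and false superiority from about 0.1% to 22%, against a nominal 2.5%. With equal mixes there is no problem.

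These figures rest on 110 and 175 independent eyes, 22% control response and the assumed shares. Correlation between a patient's two eyes is a separate matter. The change should be made, and made before results are seen, because a choice of adjustment after the imbalance is known would not be credible.

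**What to change.** Before database lock:

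1. **SAP 12.1.** Add the eye's baseline VA to the primary model in two terms: the SAP 16 category (<1.0; 1.0–1.68; off-chart, including any value above 1.68) and linear logMAR. Code off-chart values as in SAP 17.2.2 (2, 2.3, 2.6, 2.9), and say that this applies to both datasets, since that section sits under natural history. Keep the three-factor model as a sensitivity analysis. List the change in SAP 14.
2. **SAP 12.1.1 and 12.2.** Use the same outcome model in the 12.1.1 multiple-imputation analysis (including its list of pooled effects) and for the eye-level composite and CRR endpoints. Analyse the maintenance component only among eyes below 1.0 logMAR at baseline, because other eyes cannot respond.
3. **Weighted analysis, SAP 12.1.1.** Use a robust variance or normalised weights.

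**Cost.** Text and code in the SAP only, which takes precedence over the protocol; baseline VA exists for every eye in the comparison. The model gains three slopes, from four to seven, against about 82 expected responders (0.22×175 + 0.40×110 = 82.5). Simulated power is not reduced. The odds ratio becomes conditional on baseline VA, so it should not be read directly against the (0.40/0.60)/(0.22/0.78) = 2.36 implied by the planning rates.
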